12.1.2 Patient Consent Form

At the time of registration, the original signed and dated patient's Informed Consent with the Experimental Subject's Bill of Rights (for the medical record). All Institutional, NCI, Federal, and State of California regulations concerning the Informed Consent form will be fulfilled. }

12.1.3 Data Collection Forms and Submission Schedule

All data will be collected in a timely manner using protocol defined electronic data capture (EDC) case report forms. Data will be accessible to study biostatisticians from the City of Hope Department of Biostatistics and stored in a secure location.

12.1.3.1 Eligibility Checklist

The Eligibility Checklist must be completed by a protocol nurse or clinical research associate and signed by a participating investigator prior to registering the patient.

12.1.3.2 *Prior Therapy and On-Study Forms*

Within two weeks of registration, the clinical research associate will submit pre-study data collection forms.

12.2 *Protocol Deviations*

The clinical research associate at COH will also submit copies to the Protocol Management Team and the COH Data and Safety Management Board.

12.2.1 Deviation Policy

In accordance with the COH Policy on Clinical Research Protocol Deviation, there will be a “no deviations” rule for this protocol. However, for subject safety or unforeseen scheduling problems, planned deviations from this protocol will be permitted in accordance with COH IRB policies and if applicable, FDA approval.

12.2.2 Reporting of Unplanned Deviations

All unplanned deviations will be reported to the COH DSMB.

12.2.3 Resolving Disputes

If there is a dispute among the persons involved in the provision of research treatment, in regard to whether a treatment deviates from the protocol, the facts of the case will be reported to the DSMB which will be serve as the arbiter of whether a deviation exists.

13.0 Data and Safety Monitoring Plan

DATA AND SAFETY MONITORING

13.1 *Definition of Risk Level*

This is a Risk Level 4 study, as defined in the “City of Hope Data and Safety Monitoring Plan”, <http://www.coh.org/dsmc/Pages/forms-and-procedures.aspx> involving a COH-held IND.

13.2 *Monitoring and Personnel Responsible for Monitoring*

The Protocol Management Team (PMT) consisting of the PI, Collaborating Investigator, CRA/protocol nurse, and statistician is responsible for monitoring the data and safety of this study, including implementation of the stopping rules for safety and efficacy.

Data and safety will be reported to the COH DSMC. Protocol specific data collection will include the following items: Adverse event reporting and quarterly safety assessment of axitinib. Reporting of data and safety to the DSMC will occur at least quarterly using the PMT report.

13.3 Definitions

Adverse event (AE) - An adverse event is any untoward medical experience or change of an existing condition that occurs during or after treatment, whether or not it is considered to be related to the protocol intervention.

•

Unexpected Adverse Event [21 CFR 312.32 (a)] – An adverse event is unexpected if it is not listed in the investigator’s brochure and/or package insert; is not listed at the specificity or severity that has been observed; is not consistent with the risk information described in the protocol and/or consent; is not an expected natural progression of any underlying disease, disorder, condition, or predisposed risk factor of the research participant experiencing the adverse event.

Expected Adverse Event - Any event that does not meet the criteria for an unexpected event OR is an expected natural progression of any underlying disease, disorder, condition, or predisposed risk factor of the research participant experiencing the adverse event

• *Serious Adverse Event (SAE) [21 CFR 312.32] is defined as any expected or unexpected adverse event that results in any of the following outcomes:*

- Death
- Is life-threatening experiences (places the subject at immediate risk of death from the event as it occurred);
- Unplanned hospitalization equal or greater than 24 hours)) or prolongation of existing hospitalization;
- A persistent or significant disability/incapacity;
- A congenital anomaly/birth defect
- Secondary Malignancy, or
- Any other adverse event that, based upon appropriate medical judgment, may jeopardize the subject’s health and may require medical or surgical intervention to prevent one of the outcomes listed above (examples of such events include allergic bronchospasm requiring intensive treatment in the emergency room or at home, blood dyscrasias or convulsions that do not result in inpatient hospitalization, or the development of drug dependency or drug abuse).

Unanticipated problem (UP) – Any incident, experience or outcome that meets all three of the following criteria:

1. Unexpected (in term nature, severity, or frequency) given the following: a) the research procedures described in the protocol-related documents such as the IRB approved research protocol, informed consent document or Investigator Brochure (IB); and b) the characteristics of the subject population being studied; **AND**
2. Related or possibly related to participation in the research (possibly related means there is a reasonable possibility that the incident, experience, or outcomes may have been caused by the drugs, devices or procedures involved in the research); **AND**
3. Suggests that the research places subjects or others at greater risk of harm (including physical, psychological, economic, or social harm) than previously known or recognized.

13.4 Reporting of Unanticipated Problems and Adverse Events

Unanticipated Problems: Unanticipated problems must be reported to the COH DSMC and IRB **within 5 calendar days** according to definitions and guidelines at <http://www.coh.org/hrpp/Pages/hrpp-policies.aspx>. Any unanticipated problem that occurs during the study conduct will be reported to the DSMC and IRB by submitting electronically in iRIS (<http://iris.coh.org>).

- *Serious Adverse Events - All SAEs occurring during this study, whether observed by the physician, nurse, or reported by the patient, will be reported according to definitions and guidelines at <http://www.coh.org/hrpp/Pages/hrpp-policies.aspx> and Table 1 below. Those SAEs that require expedited reporting will be submitted electronically in iRIS (<http://iris.coh.org>).*

Adverse Events - Adverse events will be monitored by the PMT. Adverse events that do not meet the criteria of serious OR are not unanticipated problems will be reported only in the continuation reports and PMT reports (see Table 1 below).

Table 1: City of Hope Adverse Event and Unanticipated Problem Reporting Timelines for the DSMC and IRB

Required Reporting Timeframe to DSMC		
Attribution	UNEXPECTED	EXPECTED
	Death while on active treatment or within 30 days of last day of treatment	
Possibly, Probably, Definitely	5 calendar days	
Unlikely, Unrelated		
	Death after 30 days of last active treatment/therapy	
Possibly, Probably, Definitely	5 calendar days	No reporting required*
Unlikely, Unrelated	No reporting required*	No reporting required*
	Grades 3 and 4 AND meeting the definition of “serious”	
Possibly, Probably, Definitely	5 calendar days	5 calendar days
Unlikely, Unrelated	5 calendar days	5 calendar days
	Grade 1 and 2 AND resulting in hospitalization [#]	
Possibly, Probably, Definitely	5 calendar days	10 calendar days
Unlikely, Unrelated	10 calendar days	10 calendar days

*Such events are not required to be reported to the DSMC. These events should be included with the SAE/AE summary provided to the DSMC in the PMT reports and to the IRB in the Annual Continuation reports.

Hospitalization = Unplanned admission equal to or greater than 24 hours

Required Reporting Timeframe to IRB of Record		
Attribution	UNEXPECTED	EXPECTED
	Death	
Possibly, Probably, Definitely	5 calendar days	Annual
Unlikely, Unrelated	Annual	Annual
	Grades 3 and 4 AND meeting the definition of a UP	
Possibly, Probably, Definitely	5 calendar days	Annual
Unlikely, Unrelated	Annual	Annual
	Grade 1 and 2 AND meeting the definition of a UP	
Possibly, Probably, Definitely	5 calendar days	Annual
Unlikely, Unrelated	Annual	Annual

ADDITIONAL REPORTING REQUIREMENTS

SAEs meeting the requirements for expedited reporting to the FDA, as defined in 21 CFR 312.32, will be reported as an IND safety report using the MedWatch Form FDA 3500A for Mandatory Reporting which can be found at: <http://www.fda.gov/Safety/MedWatch/HowToReport/DownloadForms/default.htm>

The PI or designee will be responsible for contacting the Office of IND Development and Regulatory Affairs (OIDRA) at COH to ensure prompt reporting of safety reports to the FDA. OIDRA will assist the PI with the preparation of the report and submit the report to the FDA in accordance with the following:

- any unexpected fatal or life threatening adverse experience associated with use of the drug must be reported to the FDA no later than 7 calendar days after initial receipt of the information [21 CFR 312.32(c)(2)];
- any adverse experience associated with use of the drug that is both serious and unexpected must be submitted no later than 15 calendar days after initial receipt of the information [21 CFR 312.32(c)(1)]

- any follow-up information to a study report shall be reported as soon as the relevant information becomes available. [21 CFR 312.32(d)(3)]

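### Section 13.4: read literally, an OR takes serious events that are not unanticipated problems, and non-serious unanticipated problems, out of the day limits set elsewhere in the section

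*Combined protocol and SAP*

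**What the plan says.** Section 13.4 gives three reporting rules, one per paragraph, followed by a table of timelines (Table 1 of that section, not the toxicity table of the same number in Section 8.1.7).

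- First paragraph, on UPs: "Unanticipated problems must be reported to the COH DSMC and IRB within 5 calendar days".
- Second paragraph, on SAEs: "All SAEs occurring during this study, whether observed by the physician, nurse, or reported by the patient, will be reported according to definitions and guidelines", with the institutional policy and Table 1 named as those guidelines.
- Third paragraph: "Adverse events that do not meet the criteria of serious OR are not unanticipated problems will be reported only in the continuation reports"; PMT reports are named too, with a pointer to Table 1.

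The DSMC part of Table 1 has rows for deaths, for Grade 3-4 serious events, and for Grade 1-2 events with hospitalization. The IRB part has rows for deaths and for UPs only, for example "Grades 3 and 4 AND meeting the definition of a UP".

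Section 13.3 defines an SAE by its outcome, whether the event was expected or not. A UP must meet three criteria at once: it is unexpected, it is at least possibly related to the research, and it points to more risk than was known. The first criterion reads "Unexpected (in term nature, severity, or frequency) given the following". Section 13.2 adds that "Reporting of data and safety to the DSMC will occur at least quarterly using the PMT report".

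**The concern.** The adverse-event sentence should catch what is left after UPs and SAEs have been dealt with. With OR it catches much more. An event goes to periodic reports only if it fails either test, so a serious event that is not a UP is caught, and so is a UP that is not serious. The preceding two paragraphs give both of these a faster route.

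The serious events to be expected in this trial include known axitinib toxicities and complications of surgery. Many will be judged expected or unrelated, so they will be SAEs without being UPs. For a non-fatal event of that kind, the DSMC entry in Table 1 is the only day-limited route to an outside body that the protocol itself states. The FDA timelines in Section 13.4 apply to unexpected events associated with the drug, and the IRB table has no row for it. What is at stake is prompt DSMC sight of such events in a study that Section 13.1 classes as Risk Level 4 under an institution-held IND.

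**Working it through.** The plan states no figure to reproduce. The check is one of logic and of counting table cells.

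**Step 1. The sentence as logic.** Let S = serious and U = unanticipated problem. The sentence sends (not S) OR (not U) to periodic reports only, which equals not (S AND U). The four classes of event are:

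| Class | OR sentence, read literally | Rest of Section 13.4 | Agree? |
|---|---|---|---|
| S and U | not caught | 5 calendar days, DSMC and IRB | yes |
| S, not U | periodic only | Table 1, DSMC limits | no |
| U, not S | periodic only | 5 calendar days, DSMC and IRB | no |
| neither | periodic only | periodic only | yes |

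Two of the four classes conflict.

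**Step 2. DSMC cells affected.** By Section 13.3 an event that is expected, or that is unlikely to be related or unrelated, is ordinarily not a UP. The entries of the three fully legible DSMC rows are:

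| DSMC row | Related, unexpected | Related, expected | Unrelated, unexpected | Unrelated, expected |
|---|---|---|---|---|
| Grade 3-4 serious | 5 days | 5 days | 5 days | 5 days |
| Grade 1-2 with hospitalization | 5 days | 10 days | 10 days | 10 days |
| Death after 30 days | 5 days | not required | not required | not required |

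- Cells: 3 rows × 4 = 12.
- Cells that are expected or unrelated: 12 − 3 = 9.
- Of these, cells with a day limit: 9 − 3 = 6 (three at 5 days, three at 10 days). These six clash with the OR sentence.
- Four of the six are unrelated cells (2 rows × 2), and they clash on any reading. The other two are related and expected, and they clash unless the frequency alone makes the event a UP.
- The three related, unexpected cells clash only where the event does not suggest greater risk.

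The Grade 1-2 row belongs here because an unplanned admission of at least 24 hours makes an event serious under Section 13.3. The row for death on or within 30 days of treatment is not counted, because its cell layout is not clear in the text reviewed.

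**Step 3. The IRB part.** It has no row for a non-fatal serious event that is not a UP, so the OR sentence removes no IRB limit for such an event. The restriction to non-fatal events is needed because the IRB death row gives 5 calendar days to an unexpected, related death. The two UP rows have 2 × 4 = 8 cells. The two that are related and unexpected say 5 calendar days, which matches the UP paragraph. The other six say Annual, and each of them is expected, unrelated or both.

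**Step 4. Longest delay.** If the OR sentence were followed alone, the DSMC would learn of the event in the quarterly PMT report: 365 / 4 ≈ 91 days at most, against 5 or 10. Section 14.2 plans 60 patients in 60 months, which is 1 a month. One quarter therefore adds 60 / 60 × 3 = 3 men, about 1.5 of them on axitinib.

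**Step 5. After the correction.** With neither S nor U in place of OR, only the last class of Step 1 goes to periodic reports. Both conflicting classes and all six clashing cells are resolved.

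**The case against.** The best defence is context. The sentence is the third of three labelled paragraphs and reads naturally as the rule for the remainder. It points to the very table it would override. The SAE paragraph says that all SAEs follow Table 1, and the table is explicit cell by cell. Staff who follow those two report on time. The PMT also watches toxicity continuously and can hold accrual under Section 14.1.2, and serious unexpected drug-associated events have their own FDA timelines. All of this stands, and it makes a drafting slip much more likely than an intended rule. It does not remove the conflict: the sentence says only, and Section 13.4 gives no order of precedence.

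Three stronger readings are tempting, and the documents do not support them.

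- A reader might infer that IRB oversight of ordinary SAEs is delayed. For non-fatal serious events that are not UPs, the IRB table sets no short limit to lose.
- A reader might infer an expected delay of about 90 days. That figure holds only if staff set aside the explicit SAE rule.
- A reader might infer that the IRB table allows a year for UPs. The six Annual cells are ordinarily empty under the UP definition. The possible exception is a listed toxicity that becomes a UP through unexpected frequency and yet sits in the expected column. Even that is doubtful. The definition of an unexpected event in Section 13.3 also covers events inconsistent with the protocol's risk information, and Section 8.1.7 includes rates in that information. An excess could therefore already count as unexpected.

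**Conclusion.** The sentence is wrong as written and should be corrected. Literally, it removes the DSMC limits in six cells of Table 1 for serious events that are not UPs, and the 5-calendar-day rule for UPs that are not serious. It also contradicts the SAE paragraph above it. For non-fatal serious events that are not UPs, the effect is confined to the DSMC. The longest delay is to the next quarterly PMT report, on a worst-case reading and at the accrual planned in Section 14.2.

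The number of events affected cannot be computed. The protocol gives Grade 3+ rates for axitinib, such as hypertension in 68 of 364 (18.7%), but grade is not seriousness, and those rates do not come from a 28-day presurgical course. The conclusion rests on the text of Sections 13.2 to 13.4 alone. The institutional policy they cite was not available and may settle precedence. The IRB table is not a separate error.

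**What to change.** Replace the sentence in Section 13.4 with: *Adverse events that are neither serious nor unanticipated problems will be reported only in the continuation reports and PMT reports; every serious adverse event follows Table 1 whether or not it is an unanticipated problem.*

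As an optional tidy-up, add that any event meeting the UP definition, including through unexpected frequency, follows the 5-calendar-day UP rule whichever column of the IRB table it falls in. Check this addition against the cited institutional policy first.

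The cost is a wording amendment. No patients, visits or procedures are added. Sites already following the SAE paragraph and Table 1 would file no more SAE reports than now; any increase would come only where the OR sentence had been taken literally.

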14.0 Statistical Considerations

14.1 Study Design

14.1.1 The study is an open label, randomized phase II assessment of axitinib as pre-surgical therapy in high risk prostate cancer. In particular, a permuted block randomization scheme will be carried out to achieve treatment/control balance. To avoid selection bias, the blocking scheme will be masked to the principal investigator. The number of blocks will be determined by stratifying high risk patients according to PSA levels (≥ 20 or not) and Gleason scores (≥ 8 or not). For each block, we will randomly choose one arrangement from all possible realizations.*Primary Endpoints*: The primary endpoint of this study is pre-metastatic niche density, as defined by the average number of VEGFR1 clusters in 8 distinct 40x microscopic fields. We will use a two sample student's T-test to compare the primary endpoint of pre-metastatic niche density in the regional lymph nodes of patients treated with axitinib, as compared to the pre-metastatic niche density in the lymph nodes of patients enrolled on the control arm. With a sample of 22 patients per group, we will have 80% power to determine significance across groups if the average niche density is 3.13 in patients in the control arm, and at most 2.19 in patients treated with axitinib, with a common standard deviation 1.43 using a one-sided t-test assuming a type I error = 10% (Calculated using nQuery Advisor 6.01) Taking this into consideration, 30 patients per group will be recruited according to an empirical replacement rate of 27%. The intention-to-treat analysis will be the primary analysis conducted to obtain unbiased comparisons between the treatment and control. In addition, some as-treated subgroup analysis would also be investigated if necessary.*Secondary Endpoints*: Toxicity, time to biochemical recurrence, time to metastatic recurrence. With respect to secondary endpoints, Cox regression will be used (with the log-rank test) to compare time to biochemical recurrence (PSA ≥ 0.2), TTP and OS in patients treated with axitinib to patients treated with surgery alone. The Chi-square test will be used to compare the pStat3, LOX expression and MDSC density in patients treated with axitinib to patients treated with surgery alone. Descriptive statistics will be used to compare serum levels of VEGF-A, sVEGFR2, PDGF-AB and pSTAT3 at various timepoints during therapy.

14.1.2 *Stopping Rules.* Toxicity will be monitored on an ongoing basis. If the number of unacceptable toxicities exceeds 1 in the first 3 patients, or exceeds 2 in the first 6 patients or more than 25% thereafter, the study will hold accrual for an amendment regarding treatment modifications or study termination. Toxicity will be graded and recorded for each patient in this population according to CTCAE 4.0. Also, a delay in surgery exceeding 7 days as a consequence of axitinib-related toxicity will be considered an unacceptable toxicity.

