The „seed-and-soil“ hypothesis was proposed by Paget in 1889, and suggests that the biological characteristics of certain tissues may foster invasion and growth of metastases. ¹ Identification of these susceptible areas, termed pre-metastatic niches, has numerous potential clinical applications. For instance, patients with more abundant niches may have increased metastatic potential – niche prevalence could therefore serve as a personalized supplement to current prognostic models. ² Alternatively, the pre-metastatic niche could act as a target of anticancer therapy, preventing metastases from developing. Treatment of patients with high-risk prostate cancer with axitinib will decrease the extent of pre-metastatic niche formation. Consequently, patients may experience improved clinical outcome (delayed biochemical recurrence and prolonged time to metastatic recurrence/overall survival (OS)).
Primary Objective:
To determine if axitinib modulates pre-metastatic niche density in patients with high-risk prostate cancer
Secondary Objective(s):

• To determine if therapy with axitinib prolongs time to biochemical recurrence• To determine if pSTAT3 in tumor tissue is associated with biochemical recurrence• To determine if MDSC recruitment in tumor tissue is associated with biochemical recurrence• To determine if lysyl oxidase (LOX) expression in tumor tissue is associated with biochemical recurrence• To evaluate time to metastatic recurrence• To evaluate the rates of urinary incontinence (grade ≥ 3) and erectile dysfunction (grade ≥ 3) associated with preoperative axitinib therapy (as defined by CTCAE 4.0 criteria)• To evaluate changes in blood-based biomarkers (pSTAT3 and selected angiogenic factors) from baseline to the time of prostatectomy
Study Design:
Open-label, randomized phase II study
Primary Endpoint and Secondary Endpoints:
Primary:

• Pre-metastatic niche density

Secondary:

 • Toxicity, time to biochemical recurrence, time to metastatic recurrence, rate of urinary incontinence, rate of erectile dysfunction
Sample Size:
44
Estimated Duration of the Study
24 months
Summary of Subject Eligibility Criteria:

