- Physical examination: to identify any changes in the subject's mental and medical conditions since baseline assessment that would make him/her ineligible for the study.
- Blood pressure measurements: subjects must have a blood pressure reading of <140/90mmHg to be eligible. If anti-hypertensives were initiated and/or dosing has been adjusted during the Baseline Period, the blood pressure must be re-assessed on two occasions consecutively that are within 1 hour. The mean SBP/DBP values from both blood pressure assessments must be <140/90mmHg in order for a subject to be eligible. ECOG PS: Any changes since baseline assessment should be recorded in the eCRF.
- Record all the medication(s) received within 2 weeks prior to the first dose of study medication and indicate if the medication is continuing.
- Obtain archived tumor tissue samples (derived from prostatic biopsy) for biomarker assessments.

Assessments while on Study

- Physical examination: to identify any changes in the subject's mental and medical conditions since baseline assessment that would make him/her ineligible for the study. This will occur at day 15 and day 28 of protocol-based therapy for patients randomized to the Axitinib arm only. Patients will then be evaluated in the clinic with a physical examination and examination for pertinent toxicities one month following prostatectomy (constituting a standard post-operative assessment), and then every 3 months, until evidence of disease progression, death, or initiation of a subsequent line of prostate cancer therapy.

- ECOG PS.
- PSA will be performed per the study calendar, section 10.0, from randomization until the development of metastatic recurrence.
- Blood will be sequestered for correlative studies (see section 10.1) at baseline and at the time of prostatectomy, as well as the post-prostatectomy follow-up visit 4 weeks following the procedure. A total of 20 mL of blood will be collected at each of these visits; 10 mL will be collected in a CPT tube for PBMC isolation and assessment, while 10 mL will be collected for assessment of selected plasma angiogenic factors. Within 4 hours of collection, this blood will be transported to the lab of [name] (Beckman Research Institute, Room 3220).
-

Post-Study Assessments

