1.2 Secondary Objectives

- 1.2.1 To determine if pre-metastatic niche density in regional LNs is associated with PFS
- 1.2.2 To determine if therapy with axitinib prolongs time to biochemical recurrence
- 1.2.3 To determine if pSTAT3 in tumor tissue is associated with biochemical recurrence
- 1.2.4 To determine if myeloid derived suppressor cell (MDSC) recruitment in tumor tissue is associated with biochemical recurrence
- 1.2.5 To determine if lysyl oxidase (LOX) expression in tumor tissue is associated with biochemical recurrence
- 1.2.6 To evaluate time to metastatic recurrence
- 1.2.7 To determine the rate of erectile dysfunction and urinary incontinence (grade ≥ 3 for both) in the setting of preoperative axitinib therapy
- 1.2.8 To evaluate changes in blood-based biomarkers (pSTAT3 and selected angiogenic factors) from baseline to the time of prostatectomy

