9.0 Correlative/Special Studies

9.1 Laboratory Correlative Studies

Analysis of pre-metastatic niche density will take place through previously reported techniques. Briefly, a total of 12 4 μ m sections of benign lymph node tissue (derived from paraffin-embedded sections) will be stained with monoclonal antibodies directed at VEGFR1 (ImClone Systems). VEGFR1 clustering will be counted within 8 distinct 40x fields, and the cluster count will be averaged.

Analysis of pSTAT3 and related mediators will be conducted through previously reported techniques. Briefly, 4 mm sections of tumor tissue (derived from paraffin-embedded sections) will be stained with monoclonal antibodies directed at IL-6R (Calbiochem) and pSTAT3 (Santa Cruz Biotechnology). Using both IPLAB and Adobe Photoshop 7.0, random x100 objective fields will be analyzed by selected a standardized color range for immunohistochemical staining. After boundary delineation, the area under the pixilation histogram will be calculated, and the total staining area will be compared to the area of total tissue.

Of note, the laboratory investigator ([name], [name], or associates) will be blinded to the patient randomization. A total of 12 unstained slides derived from tumor and 12 unstained slides derived from normal lymph node tissue will be requested. These slides will be marked with a unique patient identifier number (UPIN) designated by the pathology core facility. Only the study PI and biostatistician will have access to the data to correlate UPIN with patient identification; this data will be housed in a password-protected electronic database.

Blood (a total of 20 mL) will be obtained at baseline, at the time of prostatectomy and at a follow-up visit 4 weeks following the procedure for correlative studies to examine levels of pSTAT3 in PMBCs and selected angiogenic markers. A total of 10 mL will be collected in a CPT tube (for PBMC isolation), and a separate aliquot of 10 mL will be collected in an EDTA tube (for assessment of angiogenic markers) at

the specified times of collection. Blood will be delivered to the lab of [name] (Beckman Research Institute, Room 3220) within four hours of collection.

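### No planned analysis relates a tissue marker to recurrence or PFS, and the chi-square test for tumour pSTAT3 needs an unstated cut-point on a continuous measure

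*Combined protocol and SAP*

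**What the plan says.** Objectives:

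- Section 1.2.3: "To determine if pSTAT3 in tumor tissue is associated with biochemical recurrence". Sections 1.2.4 and 1.2.5 ask the same for MDSC and LOX. The synopsis repeats all three, for example "To determine if MDSC recruitment in tumor tissue is associated with biochemical recurrence".
- Section 1.2.1: "To determine if pre-metastatic niche density in regional LNs is associated with PFS". The synopsis list omits this objective, and section 11 defines biochemical recurrence, metastatic recurrence and overall survival but not PFS.

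Analyses in section 14.1.1:

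- A t-test of niche density between arms (the primary analysis).
- "Cox regression will be used (with the log-rank test) to compare time to biochemical recurrence", TTP and OS between axitinib and surgery alone.
- "The Chi-square test will be used to compare the pStat3, LOX expression and MDSC density in patients treated with axitinib", again against surgery alone. No categories or threshold are given.
- Descriptive statistics for blood markers over time.

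Measurement, section 9.1: for tumour pSTAT3, "the total staining area will be compared to the area of total tissue". The only tumour antibodies named are those to IL-6R and pSTAT3, in an account that opens "Analysis of pSTAT3 and related mediators will be conducted through previously reported techniques". No scale is given for LOX or MDSC.

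**The concern.** A difference between arms in a marker does not show that the marker is associated with recurrence. Nor does a difference between arms in recurrence say anything about the marker. Followed as written, the plan asks whether axitinib changes the markers and whether it changes outcome, and gives no estimate for objectives that ask whether marker and outcome go together.

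The planned arm comparison has a second weakness. A chi-square test needs categories. For a stained-area ratio someone must choose a threshold, and if it is not fixed in advance it can be chosen after the data are seen. Splitting the ratio also discards information in a trial with 22 to 30 patients per arm.

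**Working it through.** **1. Objectives set against analyses**

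| Objective | Question | Matching analysis in 14.1.1 |
|---|---|---|
| 1.2.1 (section 1.2 only) | niche density and PFS | none |
| 1.2.2 | axitinib and biochemical recurrence | Cox/log-rank by arm |
| 1.2.3 | tumour pSTAT3 and recurrence | none |
| 1.2.4 | tumour MDSC and recurrence | none |
| 1.2.5 | tumour LOX and recurrence | none |
| 1.2.6 | time to metastatic recurrence | listed as a secondary endpoint; not in dispute |
| 1.2.7 | erectile dysfunction, incontinence | toxicity rates; not in dispute |
| 1.2.8 | blood markers over time | descriptive statistics |

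The unmatched objectives number 4 of 8 in section 1.2, or 3 of 7 in the synopsis. The Cox model in section 2.7 belongs to a separate retrospective study of 46 patients and plans nothing for this trial.

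**2. The plan's own power figure**

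Inputs from section 14.1.1: means 3.13 and 2.19, SD 1.43, 22 per arm, one-sided 10%.

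- d = (3.13 − 2.19)/1.43 = 0.94/1.43 = 0.657.
- Noncentral t with 42 degrees of freedom and noncentrality 0.657 × √(22/2) = 2.18: power 81.0%. With 21 per arm it is 79.6%.

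The stated 80% reproduces. It concerns niche density only.

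**3. Illustration: cost of splitting pSTAT3 in the arm comparison**

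The documents give no effect size or alpha for the markers. I assume normal data, a split at the pooled median, and the primary endpoint's d = 0.657 and one-sided 10%. The statistic is the signed root of the uncorrected chi-square, z = (difference in proportions)/√(2 × 0.25/n).

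- n = 22: 14 against 8 in the lower half gives z = 0.273/0.151 = 1.81, and 13 against 9 gives 1.21. The critical value is 1.282, so rejection needs at least 14 of 22. Exact size 0.0654.
- n = 30: 18 against 12 gives z = 0.200/0.129 = 1.55, and 17 against 13 gives 1.03. Rejection needs at least 18 of 30. Exact size 0.0982.

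| Per arm | Chi-square power | t-test power at the same size | Loss |
|---|---|---|---|
| 22 | 0.591 | 0.739 | 14.8 points |
| 30 | 0.771 | 0.892 | 12.1 points |

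A simulation of 200,000 trials gave chi-square power of 0.590 and 0.772. For d from 0.5 to 0.8 the size-matched loss is 12.3 to 14.8 points at 22 per arm and 8.2 to 13.5 at 30.

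**4. What the missing models could detect**

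For a Cox model with one continuous marker, the detectable HR per SD at 80% power and two-sided 5% is exp((1.960 + 0.842)/√E), where E is the number of events. The documents give no event count, so E is assumed.

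- E = 10 (17% of 60 patients, 23% of 44): exp(2.802/3.162) = 2.43.
- E = 20 (33% of 60, 45% of 44): exp(2.802/4.472) = 1.87.

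Forty events would need 40/60 = 67% or 40/44 = 91% of patients to recur. These HRs are before adjustment for arm.

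**The case against.** The case on the other side has weight in four places.

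- *These are correlative objectives.* The markers are in neither list of secondary endpoints, their assays sit under correlative studies, and the trial is not powered for them. That limits how much the gap matters. It does not close it, because they are stated objectives in two places.
- *A statistician would fit a Cox model anyway.* Probably, but marker scale, adjustment, specimen and the handling of later treatment would all stay open.
- *The laboratory is blinded to arm.* That protects the readings. It does not fix the cut-point, since the PI and biostatistician can link slides to patients.
- *The power figures are borrowed.* True. A stained-area ratio is bounded, a chi-square is usually non-directional, and the effect size and alpha belong to another endpoint. The figures show the direction and rough size of the loss in the arm comparison. They do not measure the main gap.

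Three stronger readings are tempting and not supported. A reader might infer that section 14.1.1 does nothing but compare arms; its last sentence describes blood markers over time, which serves objective 1.2.8. A reader might infer that chi-square is also wrong for LOX and MDSC, or that neither will be measured; their scales are not stated and section 9.1 is an abbreviated account, so neither inference is shown. A reader might infer harm to the primary analysis; there is none.

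**Conclusion.** The gap stands on reading alone. No analysis in section 14.1.1 relates a tissue marker or niche density to an outcome, so 4 of the 8 objectives in section 1.2 (3 of 7 in the synopsis) have no matching analysis. For pSTAT3, the planned chi-square also requires an unstated split of a continuous measure. Under the assumptions in the working, that split costs about 15 points of power at 22 per arm and 12 at 30. The change should be made, but the matter is confined to correlative objectives.

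**What to change.** 1. In section 14.1.1, compare pSTAT3 between arms, and any other marker on a continuous scale, with a t-test, linear model or Wilcoxon test. Keep chi-square only for a marker scored in categories fixed in advance. This requires stating the LOX and MDSC scales.
2. For objectives 1.2.3 to 1.2.5, add an exploratory Cox model of time to biochemical recurrence for each marker. Enter the marker as continuous where its scale is continuous, adjust for arm, and report the HR with its confidence interval. Name the specimen: the synopsis says "Obtain archived tumor tissue samples (derived from prostatic biopsy) for biomarker assessments", while both calendars also list collection of tumour specimens, and prostatectomy tissue follows axitinib in the treated arm. State how the analysis handles androgen deprivation or radiation started after surgery but before PSA recurrence, which section 6.6.4 allows.
3. Reconcile objective 1.2.1 with the synopsis. If it stands, define PFS and fit the same type of model for niche density. Substituting biochemical recurrence as the outcome would change the objective rather than analyse it.

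The cost is wording plus three exploratory models, or four if 1.2.1 stands. Sample size and the primary analysis do not change. Precision will be low: with an assumed 10 to 20 events, only an HR per SD of about 2.4 to 1.9 is detectable before adjustment, and at 10 events a model with marker and arm is already thin. That should be said in the plan, and the results reported as estimates rather than tests.
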